6.3.5 Metabolic Disorders or Events

| Event | Management |
|-----------------------------|--|
| Hyperglycemia, Grade 1 or 2 | 
 ● Continue atezolizumab and tiragolumab. ● Investigate for diabetes. If patient has Type 1 diabetes, treat as grade 3 event. If patient does not have Type 1 diabetes, treat as per institutional guidelines. ● Monitor for glucose control. |
| Hyperglycemia, Grade 3 or 4 | 
 ● Withhold atezolizumab and tiragolumab. ● Initiate treatment with insulin. ● Monitor for glucose control. ● Resume atezolizumab and tiragolumab when symptoms resolve and glucose levels are stable. |

6.3.6 Eye Disorders or Events

An ophthalmologist should evaluate visual complaints (e.g., uveitis, retinal events). Management guidelines for ocular events are provided in the table below.

Management Guidelines for Eye Disorders or Events

| Event | Management |
|------------------------|--|
| Eye disorders, Grade 1 | 
 ● Continue atezolizumab and tiragolumab. ● Patient referral to ophthalmologist is strongly recommended. |

| Event | Management |
|-----------------------------|---|
| | 
 ● Initiate treatment with topical corticosteroid eye drops and topical immunosuppressive therapy. ● If symptoms persist, treat as a Grade 2 event. |
| Eye disorders, Grade 2 | 
 ● Withhold atezolizumab and tiragolumab for up to 12 weeks after event onset.^a ● Patient referral to ophthalmologist is strongly recommended. ● Initiate treatment with topical corticosteroid eye drops and topical immunosuppressive therapy. ● If event resolves to Grade 1 or better, resume atezolizumab and tiragolumab.^b ● If event does not resolve to Grade 1 or better while withholding atezolizumab and tiragolumab, permanently discontinue atezolizumab and tiragolumab and contact PI.^c |
| Eye disorders, Grade 3 or 4 | 
 ● Permanently discontinue atezolizumab and tiragolumab and contact PI.^c ● Refer patient to ophthalmologist. ● Initiate treatment with corticosteroids equivalent to 1–2 mg/kg/day oral prednisone. ● If event resolves to Grade 1 or better, taper corticosteroids over ≥ 1 month. |

^a Atezolizumab and tiragolumab may be withheld for a longer period of time (i.e., ≥ 12 weeks after event onset) to allow for corticosteroids (if initiated) to be reduced to the equivalent of ≤ 10 mg/day oral prednisone. The acceptable length of the extended period of time must be based on the investigator's benefit-risk assessment and in alignment with the protocol requirements for the duration of treatment and documented by the investigator.

^b If corticosteroids have been initiated, they must be tapered over ≥ 1 month to the equivalent of ≤ 10 mg/day oral prednisone before atezolizumab and tiragolumab can be resumed.

^c Resumption of atezolizumab and tiragolumab may be considered in patients who are deriving benefit and have fully recovered from the immune-mediated event. The decision to re-challenge patients with atezolizumab should be based on the investigator's benefit-risk assessment and documented by the investigator.

6.3.7 Immune-Mediated Cardiac Events

IMMUNE-MEDIATED MYOCARDITIS

Immune-mediated myocarditis should be suspected in any patient presenting with signs or symptoms suggestive of myocarditis, including, but not limited to, laboratory (e.g., B-type natriuretic peptide) or cardiac imaging abnormalities, dyspnea, chest pain, palpitations, fatigue, decreased exercise tolerance, or syncope. Myocarditis may also be a clinical manifestation of myositis or associated with pericarditis (see section on pericardial disorders below) and should be managed accordingly. Immune-mediated myocarditis needs to be distinguished from myocarditis resulting from infection (commonly viral, e.g., in a patient who reports a recent history of gastrointestinal illness), ischemic events, underlying arrhythmias, exacerbation of preexisting cardiac conditions, or progression of malignancy.

All patients with possible myocarditis should be urgently evaluated by performing cardiac enzyme assessment, an ECG, a chest X-ray, an echocardiogram, and a

cardiac MRI as appropriate per institutional guidelines. A cardiologist should be consulted. An endomyocardial biopsy may be considered to enable a definitive diagnosis and appropriate treatment, if clinically indicated.

Patients with signs and symptoms of myocarditis, in the absence of an identified alternate etiology, should be treated according to the guidelines in the table below.

IMMUNE-MEDIATED PERICARDIAL DISORDERS

Immune-mediated pericarditis should be suspected in any patient presenting with chest pain and may be associated with immune-mediated myocarditis (see section on myocarditis above).

Immune-mediated pericardial effusion and cardiac tamponade should be suspected in any patient presenting with chest pain associated with dyspnea or hemodynamic instability.

Patients should be evaluated for other causes of pericardial disorders such as infection (commonly viral), cancer related (metastatic disease or chest radiotherapy), cardiac injury related (post myocardial infarction or iatrogenic), and autoimmune disorders, and should be managed accordingly.

All patients with suspected pericardial disorders should be urgently evaluated by performing an ECG, chest X-ray, transthoracic echocardiogram, and cardiac MRI as appropriate per institutional guidelines. A cardiologist should be consulted. Pericardiocentesis should be considered for diagnostic or therapeutic purposes, if clinically indicated.

Patients with signs and symptoms of pericarditis, pericardial effusion, or cardiac tamponade, in the absence of an identified alternate etiology, should be treated according to the guidelines in the table below. Withhold treatment with atezolizumab for Grade 1 pericarditis and conduct a detailed cardiac evaluation to determine the etiology and manage accordingly.

Management Guidelines for Immune-Mediated Cardiac Events

| Event | Management |
|---|--|
| Immune-mediated myocarditis, Grades 2-4 | 
 ● Withhold atezolizumab and tiragolumab for up to 12 weeks after event onset and contact PI. ● Refer patient to cardiologist. ● Initiate treatment as per institutional guidelines and consider antiarrhythmic drugs, temporary pacemaker, ECMO, VAD, or pericardiocentesis as appropriate. |
| Immune-mediated pericardial disorders, Grades 2-4 | 
 ● Initiate treatment with corticosteroids equivalent to 1–2 mg/kg/day IV methylprednisolone and convert to 1–2 mg/kg/day oral prednisone or equivalent upon improvement. ● If event does not improve within 48 hours after initiating corticosteroids, consider adding an immunosuppressive agent. ● If event resolves to Grade 1 or better, taper corticosteroids over ≥ 1 month. |

ECMO = extracorporeal membrane oxygenation; VAD = ventricular assist device.

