5.2 Study Intervention Administration

Consenting and eligible patients will undergo a blood draw to test for ctDNA 4 to 12 weeks after surgery. Twenty mL of blood will be drawn into 2 10-mL Streck tubes as described in Section 9.0.

During stage 1 of the study, patients who are ctDNA-positive will be randomized on a 1:1 basis either to receive atezolizumab + tiragolumab or atezolizumab alone. If, after analysis of stage 1 data, it is determined that enrollment will continue to stage 2, all patients will receive atezolizumab + tiragolumab.

Atezolizumab is given as an IV infusion every 4 weeks at a dose of 1680 mg over 60 minutes (+/- 15 minutes). If this rate of infusion is tolerated without an infusion-related reaction, subsequent infusions of atezolizumab may be given over 30 minutes (+/- 10 minutes). Otherwise, the rate of infusion remains 60 minutes (+/- 15 minutes). After the first infusion of atezolizumab, the patient begins a 60-minute observation period during which vital signs should be recorded at 30 (+/-10 minutes) after infusion. If the patient tolerated the first infusion well without infusion-associated adverse events, the observation period after the next and following infusions may be reduced to 30 minutes. If the patient experienced infusion-associated adverse events in the previous infusion, the observation period should be 60 minutes. If clinically indicated, vital signs should be recorded at 30 (+/- 10) minutes after the infusion of atezolizumab.

Tiragolumab is given as an IV infusion every 4 weeks at a dose of 840 mg over 60 minutes (+/- 15 minutes). If this rate of infusion is tolerated without an infusion-related reaction, subsequent infusions of tiragolumab may be given over 30 minutes (+/- 10 minutes). Otherwise, the rate of infusion remains 60 minutes (+/- 15 minutes). After the first infusion of tiragolumab, the patient begins a 60-minute observation period during which vital signs should be recorded at 30 (+/-10 minutes) after infusion. If the patient tolerated the first infusion well without infusion-associated adverse events, the observation period after the next and following infusions may be reduced to 30 minutes. If the patient experienced infusion-associated adverse events in the previous infusion, the observation period should be 60 minutes. If clinically indicated, vital signs should be recorded at 30 (+/- 10) minutes after the infusion of tiragolumab.

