6.2 Treatment Interruptions

Study treatment may be temporarily suspended as appropriate for management of toxicity. On the basis of the available characterization of mechanism of action, tiragolumab may cause adverse events similar to but independent of atezolizumab, may exacerbate the frequency or severity of atezolizumab related adverse events, or may have non overlapping toxicities with atezolizumab. Because these scenarios may not be distinguished from one another in the clinical setting, immune mediated adverse events should generally be attributed to both study drugs, and dose interruptions or treatment discontinuation in response to immune mediated adverse events should be applied to both atezolizumab and tiragolumab.

In the adjuvant setting, atezolizumab and tiragolumab may be held for a maximum of 12 weeks. If tiragolumab is interrupted for > 12 weeks for any reason, the patient must permanently discontinue tiragolumab treatment, but may continue atezolizumab if there is no contraindication and after discussion with the PI to determine whether the toxicity is considered related to tiragolumab and/or to the combination. An exception can be made if in the judgment of the investigator, the patient is likely to derive clinical benefit from resuming tiragolumab after a hold of > 12 weeks. In this case, tiragolumab may be restarted with the approval of the PI. If atezolizumab is interrupted for > 12 weeks, the patient must permanently discontinue atezolizumab. However, if, in the judgment of the investigator, the patient is likely to derive clinical benefit from atezolizumab after a hold of > 12 weeks, atezolizumab may be restarted with the approval of the PI. Continued dosing of patients with single agent atezolizumab will require that all other study eligibility criteria continue to be met. Continued administration of single agent tiragolumab after permanent discontinuation of atezolizumab is not permitted.

If a patient must be tapered off steroids used to treat adverse events, atezolizumab and/or tiragolumab may be withheld for additional time beyond > 12 weeks from the last dose until steroids are discontinued, or until steroids are reduced to prednisone dose (or dose equivalent) ≤ 10 mg/day. The acceptable length of interruption will depend on an agreement with the PI.

Dose interruptions for reason(s) other than toxicity may be allowed with PI approval.

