| Hyperthyroidism, Grade 1 | 
TSH \geq 0.1 mU/L and $<$ 0.5 mU/L:
 
 ● Continue atezolizumab and tiragolumab. ● Monitor TSH every 4 weeks. ● Consider patient referral to endocrinologist 
TSH $<$ 0.1 mU/L:
 
 ● Follow guidelines for Grade 2 hyperthyroidism. ● Consider patient referral to endocrinologist |
| Hyperthyroidism, Grade 2 | 
 ● Consider atezolizumab and tiragolumab. ● Initiate treatment with anti-thyroid drug such as methimazole or carbimazole as needed. ● Consider patient referral to endocrinologist. ● Resume atezolizumab and tiragolumab when symptoms are controlled and thyroid function is improving. |
| Grade 3 and 4 hyperthyroidism | 
 ● Withhold atezolizumab. ● Initiate treatment with anti-thyroid drug such as methimazole or carbimazole as needed. ● Refer to an endocrinologist. ● Resume atezolizumab and tiragolumab when symptoms are controlled, and thyroid function is improving. ● Permanently discontinue atezolizumab.^c |
| Adrenal insufficiency, Grade 2–4 | 
 ● Withhold atezolizumab and tiragolumab for up to 12 weeks after event onset.^a ● Refer patient to endocrinologist. ● Perform appropriate imaging. ● Initiate treatment with corticosteroids equivalent to 1–2 mg/kg/day IV methylprednisolone and convert to 1–2 mg/kg/day oral prednisone or equivalent upon improvement. ● If event resolves to Grade 1 or better and patient is stable on replacement therapy, resume atezolizumab and tiragolumab.^b ● If event does not resolve to Grade 1 or better or patient is not stable on replacement therapy while withholding atezolizumab and tiragolumab, permanently discontinue atezolizumab and tiragolumab and contact PI.^c |
| Hypophysitis (panhypopituitarism), Grade 2 or 3 | 
 ● Withhold atezolizumab and tiragolumab for up to 12 weeks after event onset.^a ● Refer patient to endocrinologist. ● Perform brain MRI (pituitary protocol). ● Initiate treatment with corticosteroids equivalent to 1–2 mg/kg/day IV methylprednisolone and convert to 1–2 mg/kg/day oral prednisone or equivalent upon improvement. ● Initiate hormone replacement if clinically indicated. ● If event resolves to Grade 1 or better, resume atezolizumab and tiragolumab.^b |

| Event | Management |
|--|---|

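### The Grade 1 pericarditis and Grade 3–4 hyperthyroidism hold lines in 6.3 name atezolizumab only, while 6.2 says interruptions for immune-mediated events should apply to both drugs

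*Combined protocol and SAP*

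**What the plan says.** **General rule.** Section 6.2 reasons that the two drugs' toxicities may not be separable in the clinic, so immune-mediated events should generally be attributed to both. It concludes that "dose interruptions or treatment discontinuation in response to immune mediated adverse events should be applied to both atezolizumab and tiragolumab". Section 5.2 is softer: if one drug is delayed for a related toxicity, delaying the other is recommended.

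**Pericarditis.** In section 6.3.7 the text above the cardiac table says "Withhold treatment with atezolizumab for Grade 1 pericarditis and conduct a detailed cardiac evaluation to determine the etiology and manage accordingly". The table itself covers only Grades 2–4. Its hold instruction, printed against immune-mediated myocarditis, names both drugs: "Withhold atezolizumab and tiragolumab for up to 12 weeks after event onset and contact PI".

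**Hyperthyroidism.** In section 6.3.4 the Grade 3 and 4 row begins "Withhold atezolizumab" and stops there. Later in the same row both drugs are resumed once symptoms are controlled and thyroid function is improving.

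**Limits on single-agent use and on holds.** Section 6.2 states: "Continued administration of single agent tiragolumab after permanent discontinuation of atezolizumab is not permitted". It also says that "atezolizumab and tiragolumab may be held for a maximum of 12 weeks", with longer holds possible for a steroid taper or with the approval of the principal investigator.

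**The concern.** The tables in 6.3 are what a site consults when an event occurs. Where a specific line there names one drug and the general rule elsewhere names two, a site can reasonably take the specific line as deliberate. The pericarditis sentence is the more exposed of the two. It is the only dosing instruction for that grade, and the table just below it names both drugs for higher-grade myocarditis. A reader could conclude that Grade 1 calls for stopping atezolizumab alone.

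At stake is a combination patient receiving tiragolumab by itself while an immune-mediated cardiac or thyroid event is being worked up or treated. Section 6.3.4 lists immune-related endocrine events as a potential risk of tiragolumab. Section 7.1.3.1 lists both pericardial disorders and hyperthyroidism as adverse events of special interest.

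**Working it through.** **Step 1. Compare the instructions.**

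| Place | Drug(s) named in the hold | Local text that fills the gap |
|---|---|---|
| 6.2, general rule | both | not needed |
| 6.3.7, Grade 1 pericarditis | atezolizumab | none |
| 6.3.7 table, Grades 2–4 myocarditis | both | not needed |
| 6.3.4, Grade 3–4 hyperthyroidism | atezolizumab | resume line in the same row names both |
| 6.3.4, Grade 3–4 hypothyroidism | both | not needed |

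The other lines in 6.3 that start a temporary hold name both drugs. The two atezolizumab-only lines therefore depart from the section's own pattern.

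**Step 2. See whether another rule closes the gap.** The ban on tiragolumab alone applies after permanent discontinuation of atezolizumab, so it does not reach a temporary hold. Section 5.2 only recommends delaying the partner drug. The instruction to hold both therefore rests on the general rule in 6.2.

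**Step 3. Bound the number of doses.** Inputs: the usual maximum hold of 12 weeks (6.2); tiragolumab 840 mg every 4 weeks (5.2); 28-day cycles (Schedule of Activities).

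- The plan's own figure: footnote 1 to the Schedule of Activities equates 12 weeks with the end of every third cycle. Check: 12 × 7 / 28 = 84 / 28 = 3 cycles. This reproduces.
- Clock from event onset: let onset be u days after the last joint dose, u = 0 to 28. Count scheduled days d = 28, 56, 84, … with u ≤ d < u + 84. For u = 0 these are days 28 and 56, which is 2 doses. For every u from 1 to 28 they are days 28, 56 and 84, which is 3 doses. So 28 of 29 onset days give 3.
- Clock from the last dose, atezolizumab resumed on day 84: days 28 and 56, which is 2 doses.
- Counting both end days can give 4, but the fourth falls on the day atezolizumab may resume, so it is not tiragolumab alone.
- A hold shorter than 4 weeks gives 0 or 1.

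The range for a standard hold is thus 0 to 3 doses, or at most 3 × 840 = 2520 mg. If both lines name both drugs, the count is 0.

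**Step 4. Count who could be exposed.** Combination patients only: 18 (stage 1) + 25 (stage 2) = 43 of 61 planned. Section 5.3 replaces stage 1 patients who stop before C3D1, so the treated number could be slightly higher. The documents give no incidence for Grade 1 pericarditis or Grade 3–4 hyperthyroidism, so the expected number of affected patients cannot be computed.

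**The case against.** The strongest reply is that silence is not permission. Neither line tells a site to give tiragolumab, and 6.2 completes both of them. That is right. A reader might infer that the protocol authorises tiragolumab alone in these two situations. It does not: that result arises only if a site sets aside 6.2 and the recommendation in 5.2.

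Second, the hyperthyroidism line is corrected by its own row, since resuming both drugs presupposes that both were held. The neighbouring Grade 2 row has also lost a word, which fits careless drafting rather than intent. This stands, and it leaves the pericarditis sentence as the one instance without a local correction.

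Third, the pericarditis hold is made while the cause is investigated, whereas the 6.2 rule concerns immune-mediated events and is qualified by the word generally. This softens the contradiction. But the reason 6.2 gives, that the drugs' effects cannot be told apart, argues as much for pausing tiragolumab during the work-up as for pausing atezolizumab.

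Fourth, three doses is a worst case. It needs a full 12-week hold, which neither line specifies, and a site that overlooks 6.2 at successive visits. Nor is it an absolute ceiling, because 6.2 allows longer holds. This also stands. A reader should not infer that three doses is the expected consequence.

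Finally, both events are reportable to Genentech within 24 hours, so they would not go unnoticed. That helps detection, but it does not tell the site which infusion to withhold.

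**Conclusion.** The inconsistency is real but narrow. Two temporary-hold lines omit tiragolumab against the general rule. The pericarditis sentence is the substantive one, and the hyperthyroidism line is a drafting slip. The governing answer is already in the protocol, so this is a correction to a safety instruction and not evidence of a missing safeguard or of established harm.

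Its size is 0 to about 3 doses of tiragolumab alone per affected patient in a standard hold. This assumes that a site follows the specific line over 6.2, keeps the 4-weekly schedule, and holds for no more than 12 weeks. Exposure is confined to the 43 planned combination patients, and how many would have these events is unknown.

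A reader might extend the point to all the other places in 6.3 that name only atezolizumab, such as the myelitis rows, the facial paresis lines, the Grade 3–4 hypothyroidism lines and footnotes c and d in 6.3.1. The documents do not support treating these as the same conflict. Where atezolizumab is permanently stopped, 6.2 already bars tiragolumab alone. Where a line continues or resumes atezolizumab, 6.2 allows atezolizumab alone in some circumstances, so leaving tiragolumab unmentioned is not a contradiction.

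The primary endpoint, the two-stage rule and the planned analyses are untouched.

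**What to change.** In the Grade 1 pericarditis sentence (6.3.7) and the Grade 3–4 hyperthyroidism hold line (6.3.4), replace atezolizumab with atezolizumab and tiragolumab. The cost is a two-line wording amendment with the usual review board approval and notice to sites.

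As a separate, optional consistency check, the sponsor could go through the remaining atezolizumab-only wording in 6.3, including footnotes c and d in 6.3.1, and state tiragolumab's status in each place. Tiragolumab should not be added by default. In particular, the Grade 3–4 hypothyroidism and hyperthyroidism rows each contain both a resume line and a permanent-discontinuation line, with no condition separating them. That condition should be written first; otherwise adding tiragolumab to the discontinuation line would make the hyperthyroidism row tell sites both to resume and to stop both drugs.

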6.3.8 Infusion-Related Reactions

No premedication is indicated for the administration of Cycle 1 of atezolizumab or tiragolumab. However, patients who experience an infusion-related reaction (IRR) or (CRS) with atezolizumab may receive premedication with antihistamines, antipyretic medications, and/or analgesics (e.g., acetaminophen) for subsequent infusions. Metamizole (dipyrone) is prohibited in treating atezolizumab-associated IRRs because of its potential for causing agranulocytosis.

IRRs are known to occur with the administration of monoclonal antibodies and have been reported with tiragolumab and atezolizumab. These reactions, which are thought to be due to release of cytokines and/or other chemical mediators, occur within 24 hours of atezolizumab or tiragolumab administration and are generally mild to moderate in severity.

Guidelines for medical management of IRRs during Cycle 1 are provided in the table below. For subsequent cycles, IRRs should be managed according to institutional guidelines.

Management Guidelines for Infusion-Related Reactions

| Event | Management |
|-------------------|---|
| IRR, Grade 1 | 
 ● Reduce infusion rate to half the rate being given at the time of event onset. ● After the event has resolved, the investigator should wait for 30 minutes while delivering the infusion at the reduced rate. ● If the infusion is tolerated at the reduced rate for 30 minutes after symptoms have resolved, the infusion rate may be increased to the original rate. |
| IRR, Grade 2 | 
 ● Interrupt infusion. ● Administer aggressive symptomatic treatment (e.g., oral or IV antihistamine, antipyretic medication, glucocorticoids, epinephrine, bronchodilators, oxygen, IV fluids). ● After symptoms have resolved to baseline, resume infusion at half the rate being given at the time of event onset. ● For subsequent infusions, consider administration of oral premedication with antihistamines, antipyretic medications, and/or analgesics and monitor closely for IRRs. |
| IRR, Grade 3 or 4 | 
 ● Stop infusion. ● Administer aggressive symptomatic treatment (e.g., oral or IV antihistamine, antipyretic medication, glucocorticoids, epinephrine, bronchodilators, oxygen, IV fluids). ● Permanently discontinue atezolizumab or tiragolumab and contact PI. ^a |

IRR = infusion-related reaction.

^a Resumption of atezolizumab or tiragolumab may be considered in patients who are deriving benefit and have fully recovered from the event. Patients can be re-challenged with atezolizumab or tiragolumab only after approval has been documented by the investigator.

